## 9. Study Subjects and Demographics

### 9.1. Disposition of Subjects and Withdrawals

All patients enrolled in the study will be accounted for. Descriptive summaries of population data will be provided overall and by age group; these will include

- The frequency and percent of patients in each analysis population, age strata and enrollment group
- The disposition of patients (including number of patients enrolled, number of patients treated, number of completers)
- study withdrawals by reason of withdrawal

### 9.2. Protocol Violations

Protocol violations will be checked on complete data for all relevant patients prior to defining the analysis populations. Relevant in this context means:

- All patients for the final analysis

The final decision regarding inclusion/exclusion of patients from the analysis sets will be taken based on protocol adherence reports during data review meetings before database lock, data release and final analysis applying the definitions in section 7.

Major protocol violations will be summarized by type of violation. Individual patients with these protocol violations will be listed.

### 9.3. Demographics and Other Baseline Characteristics

Descriptive summaries of the demographic and other baseline characteristics will be completed for the populations specified below, overall and by age group as applicable; these include:

- Demographics (Age, Gender, Race/Ethnicity, Height, Weight, BMI (calculated), ABO Rhesus blood type)

(SAF, FAS, PP)

- Medical History (SAF)

*Medical history will be coded with the Medical Dictionary for Regulatory Activities (MedDRA, according to the version specified in the Data Management Plan). Incidences of findings in medical history will be summarized by MedDRA system organ class (SOC) and preferred term (PT)*

- Prior and Concomitant Medications (SAF)

*Medications will be coded using the WHO Drug Dictionary (according to the version specified in the Data Management Plan). Incidences of prior and concomitant medications will be summarized by ATC level 2 and ATC level 4*

- Baseline Physical Examination, including vital signs (SAF)

General patient characteristics and background assessments already available in the SCGAM-01 database will be copied to the SCGAM-03 database for analysis; this includes demographics, medical history, previous and ongoing therapies.

#### **9.4. Measurement of Treatment Compliance**

The following parameters will be listed and summarized per patient and/or per infusion:

- Body weight
- Actual dose (total and per kg body weight, based on the latest available weight measurement)
- Total dose of *octanorm* administered
- Total number of infusions administered
- Total volume of solution administered
- Infusion times
- Overall amount of product administered (only included in data listings)
- Maximal volume administered (in total and per kg body weight)
- Infusion flow rates (overall and per site) (center visits only)
- Number of infusion parts administered per infusion (center visits only)
- Number of infusion lines used simultaneously (center visits only)

Deviations from the planned treatment schedule will be summarized by counting the number of infusions that deviate from the scheduled intervals by more than 2 days, and by listing all cases with more than two days deviation individually.

## 10. Efficacy Analysis

No confirmatory efficacy analysis will be performed.

The rate of SBI per person-year (bacterial pneumonia, bacteraemia/sepsis, osteomyelitis/septic arthritis, visceral abscess, bacterial meningitis) during the treatment period with octanorm will be presented as point estimates of the rate along with a two-sided 98% CI. Calculation of this CI will account for intra-patient correlation in incidents following a compound Poisson process model. Furthermore, all observed SBIs will be listed individually and in full detail.

In case no serious bacterial infections are observed, it is not possible to calculate a confidence interval with the originally planned method using compound Poisson process model; if this happens, two additional analyses will be presented as sensitivity analyses:

1. The originally planned two sided 98% confidence interval will be calculated for the worse case that one bacterial infections would have been observed.
2. The confidence interval will be calculated using a standard Poisson distribution; this second model will also be used as a sensitivity analysis if a very small number of serious bacterial infections is observed, as within patient correlations are negligible for small number of serious bacterial infections.

The annual rate of all infections of any kind or seriousness will also be presented as point estimate, but along with the two-sided 90% CI. This CI will be calculated using a compound Poisson process model to account for intra-patient correlation in incidents as described above; in addition, and as a sensitivity analysis, the same CI will be calculated using the overdispersed Poisson regression model by means of the SAS procedure GENMOD.

The duration of infection will be summarised by standard descriptive statistics by type of infection and by severity. The individual characteristics of each infection, including the time to resolution will be listed.

The use of antibiotics will be reported as a detailed list of all such medications, and the number of patients treated with antibiotics, the number of treatment episodes and the number of treatment days will be tabulated.

The QoL data will be presented descriptively by visit, along with the change from baseline (i.e. screening visit).

All absences from work or school will be listed with duration and reason for absence. The individual absence rates per person-year will calculated and summarized by descriptive statistics, including the two-sided 90% confidence interval, again calculated on basis of the compound Poisson process model.

All hospitalizations will be listed with duration and indication for the inpatient hospital stay. The individual hospitalizations days per person-year will calculated and summarized by descriptive statistics, including the two-sided 90% confidence interval, again calculated on basis of the compound Poisson process model.

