9.2.2 Efficacy Analysis Plan

No confirmatory efficacy analysis will be performed.

The rate of SBI per person-year (bacterial pneumonia, bacteremia/sepsis, osteomyelitis/septic arthritis, visceral abscess, bacterial meningitis) during the treatment period with Octanorm will be presented as point estimates of the rate along with a 99% CI. Calculation of this CI will account for intra-patient correlation in incidents following a compound Poisson process model. Furthermore, all observed SBIs will be listed individually and in full detail.

The duration of infection will be summarized by standard descriptive statistics by type of infection and by severity. The individual characteristics of each infection, including the time to resolution will be listed.

The use of antibiotics will be reported as a detailed list of all such medications, and the number of patients treated with antibiotics, the number of treatment episodes and the number of treatment days will be tabulated.

The FDA Guidance for Industry suggests that, based on historical data, a statistical demonstration of a serious infection rate per person-year less than 1.0 is adequate to provide substantial evidence of efficacy.[22] Therefore, this background information will be used for a descriptive evaluation of the serious infection rate in this extension study. Exploratory statistical testing may be performed if considered appropriate.

The QoL data will be presented descriptively by visit, along with the change from baseline (defined as the first infusion).

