##### 3.2.2. Secondary Target Variables

Secondary assessment criteria will be for quality of life and efficacy:

- QoL assessments using the CHQ-PF50 from parent or guardian of patients <14 years of age and the SF-36 Health Survey in patients ≥14 years of age. Age here refers to the age at enrollment into study SCGAM-01, so that each patient will continue using the same questionnaire as before.
- Total IgG trough levels.
- Occurrence of serious bacterial infections (SBIs) as defined in Section 10.
- The annual rate of all infections of any kind or seriousness.
- Time to resolution of infections.
- Use of antibiotics (number of days and annual rate).
- Missed days from work/school/kindergarten/day care.

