## 8. General Issues for Statistical Analysis

Descriptive summaries will be presented for each of the primary and secondary variables. In general, summaries will be completed for all patients overall and by age group as described in section 4.2.

Continuous, quantitative variable summaries will in general include the number of patients with non-missing values (N), mean, standard deviation, median, minimum and maximum, 1st and 3rd quartile.

Categorical, qualitative variable summaries will include the frequency and percentage of patients who are in the particular category. In general the denominator for the percentage calculation will be based upon the total number of patients in the analysis population unless otherwise specified.

Whenever appropriate, the analyses will be stratified according to the predefined age groups taken from the SCGAM-01 study (2 to <6 |  $\geq 6$  to <12 |  $\geq 12$  to <17 |  $\geq 17$  to  $\leq 75$ ).

Additionally, for primary and secondary endpoints, the following subgroups will be investigated:

- Male vs female subjects
- A different definition of age groups: 2 to < 12, 12 to < 17, 17 to 65, and > 65 years

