### 8.3. Handling of Missing Data

In general, missing data will not be imputed: calculations pertaining to person-year computations will be based on observed values only.

For missing weight measurements the last available body weight will be used for all calculations related to dosing; in individual patient data listings missing data will however not be replaced by imputed values.

No analyses of the patterns of missing data will be done.

For adverse events the following will be applied:

An Adverse Event (AE) is defined as treatment-emergent, if first onset or worsening is after start of the first infusion of *octanorm*.

If the start date and time of an AE are partially or completely missing, the AE will be assumed to be treatment-emergent if it cannot be definitely shown that the AE did not occur or worsen during the treatment emergent period (worst case approach). Missing dates and times will not be replaced.

For medications the following will be applied: A medication will be assumed to be concomitant if it cannot be definitely shown that the medication was not administered during the *octanorm* treatment period as defined in section 8.4 below. Missing dates will not be replaced.

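### Time to resolution of infections is planned only as a summary of durations, with no rule for unresolved infections, so the duration tables would tend to run short; the effect is small for acute infections and material only for slow-resolving types or short stays

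*SAP*

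**What the plan says.** SAP 3.2.2 names "Time to resolution of infections" among the secondary variables, and Protocol 3.1.2 does the same. Protocol 7.2 asks for it both for serious bacterial infections and for all other infections.

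The analysis is one sentence in SAP 10: "The duration of infection will be summarised by standard descriptive statistics by type of infection and by severity". Protocol 9.2.2 says the same. The next sentence in SAP 10 adds a listing: "The individual characteristics of each infection, including the time to resolution will be listed". No time-to-event estimate and no censoring rule appear in either document, and SAP 8.4, which sets out derived variables, does not define duration of infection.

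Three general rules bear on an infection without an end date:

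- SAP 8.3: "In general, missing data will not be imputed: calculations pertaining to person-year computations will be based on observed values only".
- SAP 8.3, in the paragraph on missing start dates of adverse events: "Missing dates and times will not be replaced".
- SAP 8: "Continuous, quantitative variable summaries will in general include the number of patients with non-missing values (N), mean, standard deviation, median".

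On follow-up, Protocol 7.3.1.5 allows an adverse event to end as recovering or as unresolved. Protocol 7.3.1.6 lets follow-up stop once the patient's condition is stable. Protocol 6.1.3 permits follow-up of ongoing events after the Termination Visit.

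**The concern.** The endpoint is a time to an event, and some infections will not have had the event when observation stops. An infection that is open at withdrawal or database lock, or closed as stable, has no duration to enter into a mean or median. If it is left out, the loss is not random: for a given onset date, a longer infection is more likely to be still open at the cut-off. The reported durations would then be too short.

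At stake are the planned tables by type and severity. With about 35 patients (Protocol) or 45 (SAP), many of those cells will be small, and one open infection can matter. SAP 8.3 also rules out any analysis of missing-data patterns, so the tables themselves need not show how many infections were left out.

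**Working it through.** **What can be reproduced.** The documents give no duration, event count or precision figure for this endpoint, so there is no stated figure to reproduce. The steps below check the direction and give a range for the size. Every duration distribution is an assumption.

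**Inputs from the documents.** Up to about 4.5 years or 234 weeks per patient (Protocol 3.2, SAP 4.1; SAP 4.1 also still mentions up to two years); about 35 patients (Protocol 9.1) or 45 (SAP 6); a background rate of 2 to 5.18 infections per patient-year (Protocol 1.1, used only for scale). Over 4.5 years this gives 35 × 4.5 × 2 = 315 to 45 × 4.5 × 5.18 ≈ 1,049 infections.

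**Direction.** With onset uniform over a stay of length T and no later follow-up, an infection of duration d < T is still open at the end with probability d/T. The chance of being left out is proportional to duration, so the resolved-only summary is biased downward.

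**Size, exponential durations with mean m.**

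- Share unresolved: (m/T)(1 − e^(−T/m)).
- Resolved-only mean: [m − 2m²/T + (m + 2m²/T)e^(−T/m)] / [1 − share unresolved].
- When e^(−T/m) is negligible, the relative bias of the mean is −q/(1 − q), with q = m/T.

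| Assumed mean m | Stay T | Unresolved | Bias of the mean |
|---|---|---|---|
| 14 d | 234 wk (1,638 d) | 14/1,638 = 0.9% | −0.9% |
| 14 d | 26 wk (182 d) | 14/182 = 7.7% | −8.3% |
| 90 d | 234 wk | 90/1,638 = 5.5% | −5.8% |
| 90 d | 52 wk (364 d) | 24.3% | −29.8% |
| 90 d | 26 wk | 42.9% | −52.0% |

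For the last row: e^(−182/90) = 0.132 and 2m²/T = 89.0, so the numerator is 90 − 89.0 + 179.0 × 0.132 ≈ 24.7. Dividing by 0.571 gives about 43 days against 90.

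**Size, lognormal durations.** Simulation, 400 runs per row, 35 patients at 2 infections a year. Days, all infections → resolved only:

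| Follow-up | Assumed median, log-SD | Unresolved | Mean | Median | Kaplan-Meier median |
|---|---|---|---|---|---|
| 4.5 y | 10 d, 0.8 | 0.8% | 13.7 → 13.6 (−0.8%) | 10.0 → 9.9 (−0.5%) | 10.0 |
| 4.5 y | 14 d, 1.0 | 1.4% | 23.0 → 22.5 (−2.5%) | 14.0 → 13.8 (−1.2%) | 14.0 |
| 4.5 y | 14 d, 1.5 | 2.5% | 43.0 → 36.4 (−15%) | 14.1 → 13.5 (−4%) | 14.1 |
| 2 y | 10 d, 0.8 | 1.9% | 13.8 → 13.5 (−1.8%) | 10.0 → 9.9 (−1.1%) | 10.0 |
| 2 y | 14 d, 1.5 | 5.8% | 43.9 → 30.7 (−30%) | 14.2 → 12.9 (−9%) | 14.2 |
| 1 y | 10 d, 0.8 | 4.0% | 13.8 → 13.3 (−3.3%) | 10.1 → 9.8 (−2.5%) | 10.1 |
| 1 y | 14 d, 1.5 | 10.3% | 41.5 → 24.9 (−40%) | 14.3 → 12.1 (−15%) | 14.2 |

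With 45 patients at 5.18 a year over 4.5 years the percentages hardly change: 0.8% to 2.6% unresolved, about 9 to 27 infections. Censoring the open infections brings the median back to within about 1% in every scenario.

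**Which infections are lost.** In the simulations the open infections last 1.8 to 7.4 times the overall mean. They are not simply the longest. Over 4.5 years with log-SD 0.8, the longest infection averages 108 days and the longest resolved one 105; with log-SD 1.5 the figures are 1,238 and 712 days.

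**With follow-up.** Adding an assumed 28 days after the end multiplies the share unresolved by e^(−28/m). For m = 14 that is 0.135. At 26 weeks, 7.7% becomes 1.0% and the bias of the mean falls from −8.3% to −3.2%. At 234 weeks, 0.1% are unresolved and the bias is −0.3%.

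**The case against.** The strongest case against has four parts.

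1. The SAP does not say that unresolved infections are excluded. It is silent, the no-imputation rule holds only in general, and the sentence on not replacing dates concerns adverse-event start dates. SAP 8.4 expects further derivations, and the table specifications are deferred to a separate document, where an unresolved count could still appear. This stands: exclusion is the natural reading, not a stated rule. But it leaves the handling of a named secondary endpoint open until after the data are in.

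2. Every infection is listed with its time to resolution, so in a study of this size a reader can find the open cases. This also stands, but a listing does not correct a biased mean or median in a table.

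3. Follow-up until resolved or stable, including after termination, would supply many end dates. This is right for acute infections, as the 28-day calculation shows. It does not help infections closed as stable, and it does little for slow ones: with a 90-day mean, e^(−28/90) = 0.73, so nearly three quarters of the open infections remain open.

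4. The study is descriptive, its primary objective is safety, and no test or threshold rests on duration. This stands and limits the importance of the point.

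The remedy also has a limit. An infection closed as stable is one that was not resolving, so censoring it may be informative and Kaplan-Meier would not fully remove the bias for that group.

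**Conclusion.** The point holds in a limited form. Both documents plan only descriptive statistics for a time-to-event endpoint, and neither covers infections without a resolution date. Followed as written, the plan would most naturally drop those infections from the tables and shorten the reported durations.

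For acute infections over 4.5 years the mean is understated by about 1%, and across all the lognormal scenarios at that length the median by at most about 4%. With a heavy-tailed duration distribution, the mean is 15% to 17% too low at 4.5 years and up to 40% too low at one year. These figures assume the duration distribution, uniform onset and no follow-up past the study, so they are worst cases for each assumed distribution.

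A reader might infer three stronger things that the documents do not support. They do not state that unresolved infections are excluded. The infections at risk are not simply the longest ones: they are longer on average, include short infections that began late, and leave out long ones that began early enough to resolve. And understatement of 30% or 52% is not an expected result: it needs a 90-day mean, stays of only 52 or 26 weeks, and no further follow-up. The documents give no 90-day duration, and most infections that Protocol 7.2 names as examples are acute.

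**What to change.** - **SAP 8.4:** define duration of infection (start date, resolution date, and status when there is no resolution date).
- **SAP 10:** for each type and severity, print the number of infections resolved and unresolved. Give the Kaplan-Meier median and quartiles of time to resolution, with unresolved infections censored at the last date known unresolved.
- **Sparse cells:** where the Kaplan-Meier estimate is not useful, show the descriptive summary with a label saying that it covers resolved infections only.
- **Infections closed as stable:** count them separately and note that their censoring may be informative.
- **Confidence intervals, if any are added:** allow for several infections per patient. The point estimates need no such adjustment.

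The cost is a few lines of SAP text and a standard procedure, with no new data collection. Some medians or upper quartiles will not be estimable in small cells, and reported durations will be slightly longer than under the present wording.

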Quality of Life: For QoL assessments, each patient will continue using the same questionnaire as before. That is, the parent or guardian of patients who were below 14 years of age when they entered the main study SCGAM-01 will continue using the Child Health Questionnaire-Parent Form (CHQ-PF50), and patients who were ≥ 14 years of age when they entered the main study will continue using the SF-36 Health Survey.	
Summary of Study Procedures and Statistical Analysis Plan	
Study Procedures: Patients will be enrolled only after written informed consent has been obtained by the patient or their legal guardian. For patients under the legal age of majority, written consent must be obtained from the parents or legal guardians. In addition, when required by the local regulatory authorities or Institutional Review Board (IRB), written assent must be obtained from children and adolescents based upon local requirements.	

Name of Sponsor/Company: OCTAPHARMA, Pharmazeutika Prod.Ges.m.b.H., [name]	
Name of Investigational Product: Octanorm	Protocol Identification Code: SCGAM-03
Name of Active Ingredient: Human Normal Immunoglobulin	Edition / Date of Protocol: October 04, 2018

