
The first study (Screening) visit of SCGAM-03 with the first Octanorm infusion will be the same visit as the visit in Week 65 (End-of-Study Visit) of the study SCGAM-01.
 
Eligible patients who have completed the SCGAM-01 study and were treated with any other commercially available SCIG before the start of the SCGAM-03 study (e.g. owing to a delay in local IRB approval for SCGAM-03) are permitted to enter the SCGAM-03 study.
 
The maximum allowed intermission of IgG treatment after completion of the SCGAM-01 study and before the start of treatment in the SCGAM-03 study is 5 weeks.
 
Patients for whom the Week 65 visit of the SCGAM-01 study is not identical to the First visit of the SCGAM-03 study will undergo a separate Screening visit with relevant screening procedures. Only after the patient's successful Screening and enrolment into SCGAM-03 study will the first infusion of Octanorm be permitted.
 
Screening visit assessments, to be performed before the First infusion, will include: physical examination (including weight); blood sampling for hematology, clinical chemistry, viral markers and trough total IgG, urine sample for urinalysis and urine pregnancy test (females of childbearing potential only), and completion of the same QoL questionnaire as used in the SCGAM-01 study. Note that these examinations will, for most patients, be performed within the framework of the main study SCGAM-01 (End-of-Study Visit in Week 65), in which case they need not be repeated at the same visit for SCGAM-03.
 
Patients will stay at the study site during the infusion, vital signs will be measured just before the start of each infusion given at the study site, then within 1 hour after the end of the infusion.
 
The patient's diary for the coming period of the home treatment will be issued to the patients. Ongoing adverse events and any relevant concomitant medications will be recorded.
 
At all subsequent study visits, the patients will undergo the following examinations at the site before the start of infusion: physical examination (including weight), blood sampling for hematology and trough total IgG, clinical chemistry, urine sample for urinalysis, with a urine pregnancy test if indicated. The patient's diary will be collected and reviewed. Other study assessments will be performed as indicated in the Flow Chart of Study Events.
 
One week after the last infusion, for both regular or premature termination, a termination visit will be performed at the site with the following assessments: physical examination (including vital signs and weight), blood sample for hematology, clinical chemistry, viral markers, and trough total IgG; urine sample for urinalysis and urine pregnancy test (females of childbearing potential only); completion of the QoL questionnaire; collection and review of the patient's diary.
 
AEs and any changes in concomitant medications will be recorded throughout the study period.
	

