2.2 Secondary Objectives

The secondary objectives of the study are:

- To assess the effect of Octanorm on quality-of-life measures.
- To obtain further data on the efficacy of Octanorm.

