3.3.2 Dosing

The equivalent monthly dose of IgG is usually determined in one of two ways:

- 1:1 dosing, wherein the monthly IVIG dose is split into four equal weekly SCIG infusions;
- AUC dosing, in which the SCIG dose is calculated from PK data to provide a monthly exposure to IgG equivalent to that with IVIG.

The former is common in Europe, while the latter is a requirement of the US FDA for SCIG labelling studies. For AUC dosing, the SCIG dose has been 1.3 or 1.5 times higher than the previous IVIG dose.[3,18,21]

Compared with weekly administration, PK modelling and simulation (completed in May 2017) predicted that administration of Octanorm 16.5% on a biweekly basis at double the weekly dose results in comparable IgG exposure [slightly higher IgG peak (C_{max}) and slightly lower trough (C_{min})].

Therefore, the proposed study design with respect to weekly or bi-weekly dosing is acceptable, having in mind that a corrected DCF will be applied once available. Appropriate dose levels will be maintained by regular monitoring of IgG trough levels.

If the exact DCF is not known, then a value of 1.5 will be used.

The patients will continue receiving the same Octanorm dose (in mg per kg body weight) as was administered at the Week 64 infusion of the SCGAM-01-study.

Dosing will take place on site at study visits, and otherwise at the patient's home, by self-administration or with assistance (relative, care giver etc.).

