## 4. Study Methods

### 4.1. Overall Study Design and Plan

Study SCGAM-03 is designed as a prospective, open-label, non-controlled, single-arm, multicentre phase III safety follow-up study with observation of patients receiving weekly or bi-weekly doses of *octanorm* over a period of up to two years.

The study will be conducted at study sites in the United States that already participated in the SCGAM-01 trial, and at study sites in Canada enrolling 'de novo' patients who are under other SCIG treatment.

Most US patients will migrate directly from the main study to the present extension study. However, some patients are expected to complete the main study before the commencement of the extension study. Therefore, the following rules are instituted:

- a) Patients who complete the main study after the start of the extension study will be required to migrate directly into the extension study, so that treatment with *octanorm* is not interrupted. (For these patients, the screening visit in the extension study will be the same as the final visit in the main study; extension-study screening tests that also constitute main-study tests for that visit do not need to be duplicated.) Use of an IgG product other than *octanorm* between the main and extension studies will disqualify a patient from entry to the extension study.
- b) Patients who completed the main study before the start of this extension study will be allowed to continue IgG treatment with any commercially available SCIG until the time when they can be treated within the extension study. In the intervening interval they must have received the commercially available SCIG at the approximately same dose which the patient had received in study SCGAM-01. (For these patients, the screening visit will be regarded as a fresh start and all screening procedures are to be conducted.)

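### The pooled QoL change from screening mixes on-Octanorm and other-SCIG baselines with no split by enrolment group, so it cannot be read as the effect of Octanorm on QoL

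*SAP*

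**What the plan says.** Protocol section 2.2 lists as a secondary objective "To assess the effect of Octanorm on quality-of-life measures"; SAP section 3.1.2 repeats it. The only QoL contrast planned is a change score. SAP section 10 states "The QoL data will be presented descriptively by visit, along with the change from baseline (i.e. screening visit", and protocol section 9.2.2 has QoL presented by visit "along with the change from baseline (defined as the first infusion". Protocol section 7.4.2 schedules QoL at screening, Week 60 and termination only, so both definitions lead to the same score.

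What that score represents depends on how the patient entered:

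- **Direct migrators.** According to the protocol synopsis (Study Procedures), the first extension visit "will be the same visit as the visit in Week 65 (End-of-Study Visit) of the study SCGAM-01". Protocol section 3.3.2 carries forward the dose that "was administered at the Week 64 infusion of the SCGAM-01-study". SAP section 4.1 adds: "Most US patients will migrate directly from the main study to the present extension study".
- **Bridged completers.** SAP section 4.1(b) and protocol section 3.2 allow some completers to use a commercial SCIG at about the same dose until they can enter, with a fresh screening visit.
- **De novo patients.** SAP sections 4.1 and 6 plan about 10 Canadian patients on other SCIG who were never in SCGAM-01. (SAP section 4.3 still describes the population as SCGAM-01 completers only.)

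SAP section 8 summarises primary and secondary variables overall, by age group (two groupings) and by sex. SAP section 9.1 mentions enrolment group, but for disposition only.

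**The concern.** The study has no control group and reports descriptively, so the baseline is the only comparator a QoL change score has. If the baseline means different things in different patients, the pooled mean has no single interpretation.

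For direct migrators, both ends of the contrast are on Octanorm, and the change shows maintenance or drift. For bridged completers it is a return to a product they had already used. Only for de novo patients does it compare scores before and after starting Octanorm. A small pooled change could mean that Octanorm does nothing for QoL, that QoL was maintained in a mostly established population, or that a change in the few new starters was diluted. The planned tables cannot separate these, yet they are the tables that would be cited against the QoL objective.

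**Working it through.** The QoL objective has no sample size, alpha or effect size, so the check traces the baseline in each group and works out how the groups are mixed.

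**Reproducing the plan's figures.** SAP section 6: 35 completers + 10 de novo = 45, as stated. Maximum stay: 4.5 years × 52 weeks = 234 weekly infusions, as stated.

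**Octanorm exposure at each QoL visit, direct migrators** (assuming weekly dosing from Week 1 of SCGAM-01):

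- Screening (extension Week 1): about 64 weeks.
- Week 60: 64 + 59 = 123 weeks.
- Termination after the longest stay: 64 + 234 = 298 weeks.

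For de novo patients, exposure at screening is zero. The synopsis lists the questionnaire among the assessments made before the first infusion.

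**Shares of the planned 45.** De novo: 10/45 = 22%. Completers: 35/45 = 78%. The documents say only that most US patients migrate directly. Applying that to all 35 completers, and taking a bare majority to all as the range:

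| Direct migrators | Share on Octanorm at baseline | Bridged + de novo | Share with other-SCIG baseline |
|---|---|---|---|
| 18 | 18/45 = 40% | 27 | 60% |
| 25 | 25/45 = 56% | 20 | 44% |
| 30 | 30/45 = 67% | 15 | 33% |
| 35 | 35/45 = 78% | 10 | 22% |

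**What the pooled mean estimates.** With group mean changes D (direct), B (bridged) and N (de novo), and complete data,

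pooled change = p_D × D + p_B × B + (10/45) × N,

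where p_D runs from 0.40 to 0.78 and p_B = 35/45 − p_D runs from 0.38 (17/45) down to 0. If rollovers were exactly stable (D = B = 0, for illustration only), the pooled change would be 0.22 × N, so a change in new starters would appear at about a fifth of its size. If rollovers drifted, the pooled figure could move with no change at all in new starters.

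These are shares of planned enrolment. Two questionnaires are in use, and the documents do not give the mix within each, or among patients still present at Week 60 and termination.

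**The case against.** The strongest reply is that this is a safety extension. QoL is secondary and everything is descriptive (protocol section 9.2). The extension screening visit is the ordinary reference for what happens during an extension, and presentation by visit shows absolute scores as well as change. Maintenance of QoL on long-term treatment is useful information. All of this stands, and the extension baseline should be kept. It does not answer the pooling, because maintenance in rollovers is itself blurred when new starters are averaged in.

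It can also be said that bridged patients differ little from direct migrators, having had only a fairly short spell on another SCIG at a similar dose. That is fair, and it makes rollover versus de novo the contrast that matters most.

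A reader might go further and infer any of three things that the documents do not support:

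- *That the analysis cannot address the objective at all.* For de novo patients, screening is a real pre-Octanorm baseline, and their change is an uncontrolled before-after comparison.
- *That the rollover change must be near zero, or that the plan throws away the first 64 weeks.* The first assumes any benefit has levelled off by Week 65, and no QoL time course is given. The second treats the SCGAM-01 observation period as part of this study; protocol section 1.3 says the SCGAM-01 results were analysed in Q1 2017.
- *That the earliest SCGAM-01 score would supply the missing answer.* The instrument is the same ("each patient will continue using the same questionnaire as before"), but neither document says when that score was taken. Because SCGAM-01 was meant to guide the switch from IV to SC treatment (protocol section 1.2), it may have been taken on IVIG, so change from it could mix product and route. QoL is also not among the data that SAP section 9.3 lists for copying from SCGAM-01.

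**Conclusion.** The point holds for the pooled change. As planned, it averages continued Octanorm, return to Octanorm and first switch to Octanorm, in proportions the documents leave open: 40% to 78% direct migrators and about 22% de novo. It cannot be read as the effect of Octanorm on QoL. For direct migrators it describes maintenance or drift after about 64 weeks of treatment; only the de novo patients give a before-after comparison from a pre-Octanorm baseline.

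This limits what can be concluded on one secondary objective. It does not touch the safety analyses.

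The conclusion assumes weekly SCGAM-01 dosing from Week 1, enrolment as planned, and the same QoL schedule for Canadian patients, whose separate protocol version was not among the documents reviewed. The 40% to 78% range is an assumption about direct migration. The mixing of baselines itself needs only that both rollover and de novo patients enrol.

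**What to change.** In SAP section 10, present QoL scores by visit and change from screening separately for direct migrators, bridged completers and de novo patients. If the bridged group proves too small, use rollover versus de novo. Show the number contributing at each visit. Label the rollover change as maintenance of QoL during the extension, and describe the de novo change as an uncontrolled before-after comparison following a switch from another SCIG. If a pooled figure is kept, state that it mixes these baselines and is not an estimate of Octanorm's effect.

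Optionally, for rollovers, also tabulate change from the earliest SCGAM-01 score on the same questionnaire, provided the sponsor confirms that it was taken before Octanorm. State with the table that this is uncontrolled and may also reflect a change of route or product. It would mean adding QoL scores to the data imported under SAP section 9.3.

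The main change needs SAP wording and a few extra descriptive tables from data already planned for collection, with enrolment group already a disposition category. No new patient procedure is required. The drawback is small groups, with about 10 de novo patients, split further by questionnaire, so the group means will be imprecise and should be reported as such.
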